## **2.3 Potential Risks and Benefits**

### **2.3.1 Potential Risks**

The risks associated with participation in the study are small. Penicillin is widely used to treat syphilis and other infections and is relatively well tolerated. All subjects in the trial will receive at least the currently recommended therapy. The most common adverse events (AEs) caused by penicillin include rash and hypersensitivity reactions. Therapeutic outcome is not a major concern, as all subjects will receive at least the Centers for Disease Control and Prevention-recommended dose of BPG for early syphilis. Subjects randomized to receive two additional injected doses of BPG will be at risk for additional discomfort and bruising at injection sites. Subjects may feel temporary pain or discomfort during blood draws, and there is a small risk of

infection at the site of the blood draw.

Information concerning subjects' sexual history is necessarily detailed given the study's objectives and may provoke some minor psychological or emotional stress when requested; subjects who receive a new diagnosis of an STI during the study may also experience minor psychological or emotional stress. Female subjects will be cautioned about the potential hazard of becoming pregnant and advised to use adequate birth control methods for the entire duration of their participation in the trial.

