### 7.1 Visit 1 – Screening and Enrollment/Baseline Visit (Day 1)

- The potential subject will be provided with a description of the study (purpose and study procedures) and asked to read the ICF or have it read to him/her. The ICF must be signed before any screening or study procedures are performed.
- Demographic information will be collected from the subject.
- Eligibility criteria will be reviewed with the subject.
  - Complete medical history will be obtained by interviewing subjects (and reviewing medical records for the past 14 days, if available) to assure eligibility. If available in the medical record, the most recent viral load result from the past six months prior to enrollment should be recorded.
  - Sexual history for the past 60 days will be collected.
  - A targeted physical examination will be performed by a qualified study clinician (including vital signs: temperature, heart rate, respiration rate, and blood pressure; and genital, rectal, oral, skin, and lymph node examinations).
  - Study staff will swab consenting subjects' oral cavities and primary or secondary lesions (if lesions are present per Section 5.1); see Section 8.2.2.
  - A urine or serum pregnancy test will be performed on all subjects of childbearing potential and must be negative prior to randomization.
  - All concomitant medications taken in the last 30 days prior to initiating BPG treatment will be recorded on the appropriate data collection form.
  - Blood will be collected for RPR test, storage, and HIV assays (including a CD4 count for persons with known HIV infection whose medical records do not include a CD4 count in the past 30 days, and an HIV test for persons who do not have a previously documented positive HIV test result). Specimens will be collected at sites of exposure for screening/diagnosis of gonorrhea and chlamydia for all subjects who have not been tested since last sexual activity and for all subjects who have been sexually active in the past 14 days and for other STIs as indicated by local standard of care and subject history. Clinicians will provide pre- and post-test counseling, treatment, and referrals per local standard of care.

At this juncture, if a potential subject is not eligible, the reason for screening failure will be recorded and the subject will not be enrolled.

- 
- Subject will be enrolled in Advantage eClinical® and randomly assigned to Arm 1 or Arm 2.

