  - BPG will be administered, and the subject will be observed per clinic standard operating procedure (SOP).
  - Study personnel will discuss with subjects and assess and record all AEs/SAEs (including solicited reactogenicity AEs and other unsolicited AEs).
  - Protocol requirements will be reviewed with the subject.
  - Contact information will be collected, the subject's preferred method of contact will be noted, and the Week 1 visit will be scheduled.
  - The Jarisch-Herxheimer checklist will be distributed and the instructions reviewed with the subject. The subject will be asked to have the completed checklist available for reference during the non-visit contact approximately 24-48 hours after Visit 1 and to bring it to Visit 2. Study personnel will instruct the subject to use a thermometer to take temperature reading(s) at home, if possible, and note the highest temperature if s/he feels feverish any time before being contacted to assess for symptoms of a Jarisch-Herxheimer reaction as described in Section 8.1. Study personnel will attempt to contact subjects by phone call, text message, or email approximately 24 hours after Visit 1 to make this assessment. Note that data will be recorded on the appropriate electronic case report forms (eCRFs) based on subject interview; the Jarisch-Herxheimer checklist completed by the subject will not be retained.

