#### **Evaluation for symptoms of a Jarisch-Herxheimer reaction**

Approximately 24 hours after Visit 1, the subjects will be contacted as noted in Section 7.1 and evaluated for symptoms of a Jarisch-Herxheimer reaction. During this assessment, subjects should refer to the completed Jarisch-Herxheimer checklist distributed at Visit 1. Subjects will be asked about fever (confirmed by thermometer at home close to the time of fever onset, if possible), chills, myalgia, weakness, flushing, worsening of skin rash, tachycardia (i.e., fast heartbeat), heart palpitations, arthralgia, nausea, headache, and dizziness, including time of onset and time of resolution of each symptom reported. If subjects cannot be reached after Visit 1, the evaluation for symptoms of a Jarisch-Herxheimer reaction will be conducted at Visit 2 (per Section 7.1, all subjects will be asked to bring the completed checklist with them to Visit 2). Data will be recorded on the appropriate eCRF(s) based on subject interview during the non-visit contact or at Visit 2 if the contact is not successful; the Jarisch-Herxheimer checklist completed by the subject will not be retained.

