### 9.2.2 Reactogenicity

Reactogenicity events are AEs that are common and known to occur for the study drug being studied. For this protocol, the following reactogenicity events are expected to occur among some subjects:

- Systemic reactions: Jarisch-Herxheimer reaction (as described in protocol Section 8.1)
- Local injection site reactions: pain or tenderness, erythema or redness, induration or swelling

Reactogenicity events (as solicited AEs), along with unsolicited AEs, will be assessed at the visits specified in protocol Section 7 and will be graded using a protocol-defined grading system (see Appendix B).

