### 11.4.3 Safety Analysis Plan

Safety evaluations will be based on the incidence, severity, and type of AEs and SAEs, as detailed in Section 9. In addition, the incidence of systemic reactions and local injection site reactions will be evaluated. Safety variables will be tabulated and presented for all subjects in the safety population, grouped by treatment.

Reactogenicity events will be analyzed by taking the most severe response over the follow-up period, dichotomizing into a binary variable (none versus mild, moderate, or severe) and using exact confidence intervals to summarize the reactogenicity rates. Tabular and graphical summaries of events will be presented for each solicited event, by type (local/systemic), severity (none, mild, moderate, severe), and time point post-dose. The proportion of subjects who experience a Jarisch-Herxheimer reaction will be summarized overall and by treatment. Logistic regression analyses may be used to determine the association of treatment with Jarisch-Herxheimer reaction after adjusting for HIV co-infection status and time point.

Unsolicited AEs and SAEs will be coded by MedDRA® for preferred term and system organ class. The rate and exact 95% confidence intervals of AEs and SAEs in aggregate, as well as by MedDRA® categories, will be computed. The number of SAEs will be reported by a detailed listing showing the type, MedDRA® coding, relevant dates (treatment dosing date(s) and SAE onset and resolution dates), severity, relatedness, and outcome for each event.

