**APPENDIX B: TABLE FOR GRADING THE SEVERITY OF ADVERSE EVENTS**

PARAMETER	GRADE 1 - MILD	GRADE 2 - MODERATE	GRADE 3 - SEVERE
Clinical adverse event NOT identified below	Mild symptoms causing no or minimal interference with usual social and functional activities with intervention not indicated	Moderate symptoms causing greater than minimal interference with usual social and functional activities with intervention indicated	Severe symptoms causing inability to perform usual social and functional activities with intervention or hospitalization indicated
Vital signs			
Temperature	38.0 to <38.6°C	38.6 to <39.3°C	≥39.3°C
Blood pressure	140 – 159 mmHg systolic OR 90 – 99 mmHg diastolic	160 – 179 mmHg systolic OR 100 – 109 mmHg diastolic	≥180 mmHg systolic OR ≥110 mmHg diastolic OR hospitalization indicated
Pulse	101-115 or 50-54 or 45-50 if baseline <60bpm	116-130 or 45-49 or 40-44 if baseline <60bpm	>130 or ventricular dysrhythmias or <45 or <40 if baseline <60bpm
Respiration	23-25	26-30	≥30
Local injection site			
Pain or tenderness (report only one)	Symptoms causing no or minimal interference with usual social and functional activities	Symptoms causing greater than minimal interference with usual social and functional activities	Symptoms causing inability to perform usual social and functional activities
Erythema or redness (report only one)	2.5 to <5 cm in greatest diameter AND Symptoms causing no or minimal interference with usual social and functional activities	≥5 to <10 cm in greatest diameter OR Symptoms causing greater than minimal interference with usual social and functional activities	≥10 cm in greatest diameter OR Ulceration OR Secondary infection OR Sterile abscess OR Symptoms causing inability to perform usual social and functional activities
Induration or swelling (report only one)	2.5 to <5 cm in greatest diameter AND Symptoms causing no or minimal interference with usual social and functional activities	≥5 to <10 cm in greatest diameter OR Symptoms causing greater than minimal interference with usual social and functional activities	≥10 cm in greatest diameter OR Ulceration OR Secondary infection OR Sterile abscess OR Symptoms causing inability to perform usual social and functional activities

Systemic			

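### Injection-site reactions, the only risk stated as greater with three doses, are solicited on the day of each dose and then not until the next visit (up to 24 days later), so short-lived reactions are dated and sized from recall

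*Protocol*

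**What the plan says.** - **The added risk.** Section 2.3.1: "Subjects randomized to receive two additional injected doses of BPG will be at risk for additional discomfort and bruising at injection sites". No other risk there is described as larger in Arm 2.
- **What is solicited.** Section 9.2.2 lists three local reactions: pain or tenderness, erythema or redness, and induration or swelling. They "will be assessed at the visits specified in protocol Section 7 and will be graded using a protocol-defined grading system". Bruising is not on the list.
- **When.** In Section 7.1 the dosing step reads "BPG will be administered, and the subject will be observed per clinic standard operating procedure (SOP", and the next step is "Study personnel will discuss with subjects and assess and record all AEs/SAEs (including solicited reactogenicity AEs and other unsolicited AEs". Sections 7.2.1 and 7.2.2 use the same order for doses 2 and 3, and Section 7.2.3 repeats the enquiry at Month 1. Appendix A marks the AE/SAE row at Visits 1 to 4 and at unscheduled visits, and leaves it blank in the Contact column.
- **The contact between visits.** Section 8.1: "Approximately 24 hours after Visit 1, the subjects will be contacted as noted in Section 7.1 and evaluated for symptoms of a Jarisch-Herxheimer reaction". The symptoms listed there contain no injection-site item. The take-home checklist serves the same assessment, and neither is repeated after doses 2 and 3.
- **Grading.** In Appendix B, Grade 1 erythema or induration needs "2.5 to <5 cm in greatest diameter" together with no or minimal interference with activities. Grades 2 and 3 can be reached by diameter or by function. Pain or tenderness is graded on function alone.
- **Analysis.** Section 11.4.3 takes the most severe response, dichotomises it as none versus mild, moderate or severe, and tabulates each solicited event "by type (local/systemic), severity (none, mild, moderate, severe), and time point post-dose".

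**The concern.** The same-day check sees only what appears before the subject leaves the clinic. A local reaction that develops later and clears before the next visit is recorded only if the subject remembers it. Its onset, duration and diameter are then recalled and not observed.

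The protocol takes more care with the Jarisch-Herxheimer reaction: a checklist, home temperature readings and a contact at about 24 hours. That outcome follows the first dose, which is the same in both arms. The reaction that the protocol expects to differ between arms is collected by the weaker method. At stake is the accuracy of the planned safety comparison of local reactions between one and three doses.

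**Working it through.** The protocol gives no figure for these intervals, so there is none to reproduce. They follow from the visit windows.

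**Inputs (Section 7 and Appendix A).** Visit 1, with dose 1, is Day 1. Visit 2, with dose 2 in Arm 2, is Day 7 to 13. Visit 3, with dose 3 in Arm 2, is 6 to 12 days after Visit 2. Visit 4 is Day 30 ± 7, that is Day 23 to 37.

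**Days from each dose to the next planned enquiry after the dosing visit**
- Dose 1 to Visit 2: 7 − 1 = 6, up to 13 − 1 = 12.
- Dose 2 to Visit 3: 6 to 12, by definition of the window.
- Dose 3 to Visit 4: Visit 3 falls between Day 7 + 6 = 13 and Day 13 + 12 = 25. The longest gap is 37 − 13 = 24 days. At the other end, 23 − 25 = −2, so the windows overlap and there is no minimum gap. Of the 7 × 7 × 15 = 735 allowed day combinations, 118 give a gap under 6 days (a count of dates, not a probability).
- Nominal timing: Visit 2 on Day 7 or 8, Visit 3 a week later on Day 14 or 15, and Visit 4 on Day 30 give 16 or 15 days after dose 3.

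**What the diameter decides.** For erythema or induration with no or minimal interference, the functional route to Grades 2 and 3 is closed. The diameter alone then decides whether the reaction reaches Grade 1, and so whether it counts as none or any in 11.4.3.

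**Illustration of direction (all rates assumed, none from the protocol).** Suppose that 30% of doses cause a local reaction, independently between doses.
- True any-reaction rates: Arm 1 0.300; Arm 2 1 − 0.7³ = 0.657; difference 35.7 points.
- 70% of reactions captured after every dose: Arm 1 0.30 × 0.7 = 0.210; Arm 2 1 − 0.79³ = 0.507; difference 29.7 points.
- 70% captured after doses 1 and 2, 50% after dose 3: Arm 1 0.210; Arm 2 1 − 0.79 × 0.79 × 0.85 = 0.470; difference 26.0 points.
- 50% captured after every dose: Arm 1 0.150; Arm 2 1 − 0.85³ = 0.386; difference 23.6 points.

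The absolute difference shrinks in each case. In the third case the proportion captured is about the same in both arms: 0.210/0.300 = 70% and 0.470/0.657 = 71%. The ratio of rates hardly moves: 0.657/0.300 = 2.19 and 0.470/0.210 = 2.24. Of the loss of about 9.8 points, about 6.0 come from uniform under-capture and about 3.8 from the longer recall after dose 3.

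**The case against.** The case for leaving the plan alone has substance.

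- **Same-day enquiry exists.** A reader who looks only at the gaps might infer that local reactions are first asked about 6 to 24 days after each dose. The protocol does not support that. Visits 1, 2 and 3 each place a solicited reactogenicity assessment after the injection.
- **Timing data are collected.** A reader might also infer that the schedule cannot supply a tabulation by time since dose. Section 9.2.1 requires onset time, resolution time and changes in severity, so the table can be made. What stands is that, for reactions between visits, its entries rest on recall.
- **The centimetre criterion has limited reach.** Grades 2 and 3 have a functional route, and pain needs no measurement. What stands is Grade 1 erythema and induration, where the diameter is a necessary condition.
- **Other routes of capture.** Visit 2 asks about medication tolerance, unscheduled visits can record AEs, and bruising can be recorded as an unsolicited AE. The Manual of Procedures and eCRFs are not shown and may hold more. These routes reduce the loss. None is a planned enquiry about injection sites between visits.
- **Proportionality.** Section 9.2.1 calls the safety profile of one and three doses well established, and no objective or outcome measure concerns local reactions. This argues against a costly remedy, but not against a few lines on a checklist that subjects already take home.

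**Conclusion.** The point holds as a cheap improvement to a descriptive safety summary. After the same-day check, no enquiry or diary for injection-site reactions is described until the next visit: 6 to 12 days after doses 1 and 2, and up to 24 days after dose 3. Reactions that come and go in that time can be missed, misdated or wrongly graded. This can understate local reaction rates and the absolute difference between arms. The size is unknown, because the protocol gives neither reaction rates nor recall rates. The trial is open-label, so reporting could also be biased in the other direction.

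Two stronger conclusions are tempting and not supported. One is that capture is proportionally worse in Arm 2 because only Arm 2 has the long recall after dose 3. The illustration shows a larger absolute loss there (about 19 points against 9) but nearly equal proportions captured. The other is that local tolerability is half of the benefit-risk question. The protocol nowhere gives it that weight. The serological primary analysis is not affected.

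Separately, bruising is named as a risk in 2.3.1 but is neither solicited in 9.2.2 nor given its own row in Appendix B. That mismatch does not depend on any argument about recall.

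**What to change.** 1. Add pain or tenderness, erythema or redness, and induration or swelling to the existing take-home checklist and to the 24-hour contact after Visit 1. Ask for the largest diameter where relevant, and for start and stop dates.
2. Mark solicited local reactions in the Contact column of Appendix A.
3. Give Arm 2 subjects the same local-reaction checklist at Visits 2 and 3, to complete at home and have transcribed to the eCRF at the next scheduled visit. The completed checklist is not retained (Sections 7.1 and 8.1), so the diameter and dates need their own eCRF fields.
4. Add bruising to the solicited local events in 9.2.2 and to the checklist, to match 2.3.1.

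The cost is a few lines on an existing checklist, contact script and eCRF, and two more paper checklists per Arm 2 subject. No visit, contact or staff is added. The downside is slightly more subject burden, and reported reaction rates will probably be higher.

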### 9.2.3 Serious Adverse Events

#### **Serious Adverse Event (SAE):**

An AE or suspected adverse reaction is considered "serious" if, in the view of either the investigator or sponsor, it results in any of the following outcomes:

- death,

- 
- a life-threatening AE\*,
  - inpatient hospitalization or prolongation of existing hospitalization,
  - a persistent or significant incapacity or substantial disruption of the ability to conduct normal life functions, or
  - a congenital anomaly/birth defect.
  - Important medical events that may not result in death, be life-threatening, or require hospitalizations may be considered serious when, based upon appropriate medical judgment, they may jeopardize the subject and may require medical or surgical intervention to prevent one of the outcomes listed in this definition. Examples of such medical events include allergic bronchospasm requiring intensive treatment in an emergency room or at home, blood dyscrasias or convulsions that do not result in inpatient hospitalization, or the development of drug dependency or drug abuse.

\* An AE is considered “life-threatening” if, in the view of either the investigator or sponsor, its occurrence places the subject at immediate risk of death. It does not include an AE that, had it occurred in a more severe form, might have caused death.

All SAEs will be:

- Assessed for severity and relationship to the study drug and alternate etiology (if not related to the study drug) by a licensed study physician.
- Recorded on the appropriate SAE form and eCRF.
- Followed through resolution by a licensed study physician.
- Reviewed and evaluated by the DSMB (periodic review unless related), DMID, and the IRB.

## 9.3 Reporting Procedures

### 9.3.1 Serious Adverse Events

SAEs will be followed until resolution even if this extends beyond the study reporting period. Resolution of an SAE is defined as the return to pretreatment status or stabilization of the condition with the expectation that it will remain chronic.

**Any AE that meets a protocol-defined serious criterion must be submitted immediately (within 24 hours of site awareness) on an SAE form to the DMID Pharmacovigilance Group, at the following address:**

---

**SAE Email Address: [REDACTED]**

Other supporting documentation of the event may be requested by the DMID Pharmacovigilance Group and should be provided as soon as possible.

The DMID Medical Monitor and Clinical Protocol Manager will be notified of the SAE by the DMID Pharmacovigilance Group. The DMID Medical Monitor will review and assess the SAE for regulatory reporting and potential impact on study subject safety and protocol conduct.

At any time after completion of the study, if the investigator becomes aware of an SAE that is suspected to be related to the study drug, the investigator will report the event to the DMID Pharmacovigilance Group.

### **9.3.2 Regulatory Reporting for Studies Not Conducted Under DMID-Sponsored IND**

As this study will not be conducted under an Investigational New Drug application (IND), MedWatch will be used only to report SAEs that are both unexpected and deemed related to the study drug. DMID should be copied simultaneously when an alternate method of reporting is utilized.

### **9.3.3 Reporting of Pregnancy**

Subjects of child-bearing potential will be counseled to continue using acceptable forms of birth control for the entire duration of their participation in the trial. If a subject becomes pregnant during the study, dosing will be discontinued immediately, and early termination assessments will be performed. A pregnancy reporting form will be completed for any study subject who becomes pregnant during study participation. The site will maintain contact with pregnant study subjects to obtain pregnancy outcome information. The pregnant subject will be followed until delivery or until the end of pregnancy (in the case of miscarriage or pregnancy termination). Infants born to these study subjects will also be monitored for SAEs (congenital anomalies or other birth defects) and other complications for up to 2 months after birth. Pregnancy reporting forms will be limited to collecting data on the following information:

- prior maternal history including congenital abnormalities or pregnancy complications;

- estimated date of conception;
- estimated and actual date of delivery or end of pregnancy;
- pregnancy outcome (live birth, stillbirth, miscarriage, or elective termination);
- mode of delivery;
- maternal complications; and
- neonatal complications (i.e., lethal or nonlethal congenital abnormality).

Pregnancies occurring in subjects will be reported via Advantage eClinical® on the Pregnancy Report form.

